Sarcopenia, a progressive and generalized skeletal muscle disorder characterized by accelerated loss of muscle mass and function, which is related to functional and physiological impairments.³ It has emerged as a public health priority which affects 10% of the general older population.⁴ Individuals with sarcopenia are associated with profound adverse health outcomes, including increased incidents of falls and fractures, functional decline and increased all-cause mortality.⁵ The prevalence of sarcopenia increases to 31.4% among the individuals with cardiovascular disease, such prevalence rate is the highest when compared to people suffering from other comorbidities, including dementia, diabetes and respiratory disease.⁶ Accumulating empirical evidence exists to indicate sarcopenia as an important prognostic factor in patients with CAD. A recent meta-analysis (N = 10) found that CAD patients with sarcopenia had more than a double of higher rate of major adverse cardiovascular outcomes (hazard ratio = 2.27, 95% confidence interval: 1.58 – 3.27) than the non-sarcopenic counterpart.⁷ The biological mechanisms underpinning sarcopenia and atherosclerosis are yet to be fully elucidated, several shared pathophysiological and behavioral pathways appear to underlie the progression of both conditions, including endothelial dysfunction, arterial stiffness, inflammation and physical inactivity.⁸ In particular, empirical studies reported more consistent association of lower limb muscle function with atherosclerosis in CAD patients, rather than the muscle function of upper limb.⁹ The potential explanation may be related to the decline in lower limb muscle function results in reduced physical activity, which then lead to progression of both sarcopenia and atherosclerosis in patients with CAD. Furthermore, skeletal muscle acts as an endocrine organ which secretes myokines during muscle contractions. This bioactive substance protects coronary arteries against progression of atherosclerosis and stabilization of atherosclerotic plaques through anti-inflammatory effects.¹⁰ Reduced myokines level jeopardizes such cardio-protective effects in sarcopenic CAD patients. Altogether, the vicious cycle between reduced muscle mass/strength and atherosclerosis underscores the urgency of managing sarcopenia in the population with CAD.

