Despite these encouraging findings on the beneficial effects of resistance-based exercise on sarcopenia and CAD separately, no study has been done to examine its effects on patients having the co-existence of sarcopenia and CAD, leaving a significant gap in the literature. Indeed, enabling this vulnerable cohort to adopt and maintain regular resistance exercise remains a great challenge. Older adults have reported perceived difficulty, time constraints and boredom as obstacles to resistance exercise.¹⁸ An effective yet sustainable intervention needs to address these challenges/obstacles. Previous studies have highlighted the importance of enhancing older people's self-efficacy in performing exercise in order to improve exercise adoption and adherence.^{19,20} Moreover, opportunities to resistance training, indeed, emerge around the clock in the routine of an individual. Assisting older adults to integrate exercise into daily activities can maximize the training benefits and overcome barriers to exercise, and thus improve exercise adoption and adherence.²¹ Therefore, this study aims to develop a strength-building lifestyle-integrated intervention for sarcopenic CAD patients and to examine the feasibility and preliminary effects of this intervention on skeletal muscle mass, muscle strength, physical performance, cardiac-related functional status and health-related quality of life (HRQoL), psychological distress, major adverse cardiovascular and cerebral events (MACCE) and hospital readmission rates. Physical performance will be the primary outcome, while the remaining will be the secondary outcomes.

Research plan and methodology

Study design

This study will include an assessor-blinded two-arm prospective pilot randomized controlled trial (RCT) and a qualitative study to determine the feasibility, acceptance and engagement experience of the participants in the strength-building lifestyle-integrated intervention with assessments measured at baseline, 3 months and 6 months after randomization.

Study setting and participants

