In the first two weeks of the familiarization phase, a community-based training will be adopted to let participants be familiar with the exercise protocol and to master the skills of the different types of resistance movements that can be done in everyday activities. The training schedule is 2 sessions per week and will take place in the community centers close to the participants' residential area in a small group format (4 participants/group). This training component will start with warm-up, followed by core exercise training, and cool-down exercise. A series of flexibility training and stretching will be performed during the warm-up and cool-down phases (15 minutes in total). The core exercise session will comprise balance and resistance (40 minutes) training, with 5 minutes break in between. The exercise protocol will include strength-building training with simple elastic equipment, such as elastic bands, cuff weights, and Gymstick™. Gymstick™ consists of a lightweight shaft and elastic tubing with foot straps connected to each end of the shaft. It is inexpensive, safe and can provide resistance training to all major muscle groups. Different resistance levels are available and the load on each Gymstick™ can be titrated by rolling the bar to shorten the elastic tubing. The resistance load will be individualized according to the periodically estimated 1-RM on a two-weekly interval. The resistance training will focus on large muscle groups over different body parts and will start with higher repetitions (e.g., 15 repetitions) at a lower intensity (30% of 1-RM) to build muscle endurance, confidence, and for mastering appropriate movement skills. This will progress to fewer repetitions (e.g., 7 – 8 repetitions) at greater intensity (i.e., 60 – 69% of 1-RM) to build muscle power. The progression will base on the OMNI scale, a validated 11-point perceived exertion scale for assessing the perceptions of exertion when performing resistance exercise.³⁰ The numbers on the scale represent a range of exertion levels from 0 (extremely easy) to 10 (extremely difficult). Patients' symptom status will also be monitored and the exercise intensity will be titrated to ensure patients are free from ischemic symptoms. Other exercise that can be integrated into everyday activities without special exercise equipment will also be included: single limb stance with and without arm, walking heel to toe, rock the boat, back leg raises, side leg raises, balancing wand, wall pushups, marching in place, toe lifts and calf stretches. Other than prescribing the number of repetitions and sets for these different forms of exercise, the participants will be equipped with the knowledge and skills about the strategies/principles to improve balance and strength in everyday activities. For instance, they are suggested to perform a tandem stance while watching television, and then upgraded to standing on one leg.

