
From Week 3 and 4, the exercise specialist will deliver supervised home-based training, with one in-person session via home visits and one session to be delivered remotely via an online platform (Zoom). Apart from ensuring the same training principles for the intensity as those in the community-based group training sessions, the exercise specialist will observe the home environment, explore the daily routine of patients and provide individualized advice on the integration of the exercise tasks into their daily activities. Then the supervision will gradually tail off from Week 5 and onwards, from online supervised sessions, to unsupervised self-practice sessions. To ensure proper progression of the training intensity, an in-person supervised home visit as a booster session will be given at Week 9, the beginning of the habituation phase. The remaining sessions in this phase will all be unsupervised self-practice sessions. Telephone follow-ups will be arranged at Week 10 – 12 by the exercise specialist, to offer continuous support and guidance to the participants. He/she will help participants to resolve any difficulties and barriers that they may encountered when integrating the exercise into their daily life. An exercise logbook will be used to document the exercise pattern of each participant.

Table 1. Schedule of the strength-building lifestyle-integrated intervention.

Phase	Week	Session 1	Session 2
Familiarization phase	1	In-person community-based exercise	In-person community-based exercise
	2	In-person community-based exercise	In-person community-based exercise
	3	In-person supervised home-based exercise	Remote supervised home-based exercise
	4	In-person supervised home-based exercise	Remote supervised home-based exercise
Consolidation phase	5	Remote supervised home-based exercise	Unsupervised home-based self-practice
	6	Remote supervised home-based exercise	Unsupervised home-based self-practice
	7	Unsupervised home-based self-practice	
	8	Unsupervised home-based self-practice	
Habituation phase	9	In-person supervised home-based exercise	Unsupervised home-based self-practice
	10	Unsupervised home-based self-practice + Tel support	
	11	Unsupervised home-based self-practice + Tel support	
	12	Unsupervised home-based self-practice + Tel support	

Fidelity monitoring and optimization

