Cardiac-specific functional status: The Seattle Angina Questionnaire will be used to measure cardiac-related functional status. It has 19 items in 5 subscales: physical limitation, angina stability, angina frequency, treatment satisfaction and disease perception.³² It is scored on a 1–5 or 6 sequentially coded scale and subscale scores are transformed to a scale of 0–100, with higher scores indicating higher levels of functioning and fewer limitations. The Chinese version has been shown to be reliable, valid, and sensitive to clinical change.³²

Cardiac-specific HRQoL: The MacNew will be used to measure cardiac-specific HRQoL.³³ It has 27 items scored on a 1-7 scale, and then global score is calculated by summing the item scores, with higher scores representing better HRQoL. MacNew has good internal consistency, test-retest reliability, concurrent and discriminant validity.³³

Psychological distress: The Patient Health Questionnaire-4 (PHQ-4)³⁴ will be used to measure psychological distress. It consists of 4 items assessing anxiety and depression, to be responded on a 4-point Likert scale. The composite total score ranges from 0 to 12, higher scores indicate greater level of anxiety and depression. It has good psychometric properties.³⁴

MACCE and hospital readmission rates: will be monitored from enrollment to the study to 3 months after the intervention through record review.

Data collection procedure and randomization

Ethical approval will be obtained from the institutional review board. Active recruitment strategies will be used by posting recruitment notes on the newsletters and Facebook of the

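### No adverse-event collection is planned, so falls, injuries and non-anginal symptoms short of MACCE or readmission are not captured in either arm

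*Combined protocol and SAP*

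**What the plan says.** The closing paragraph of the Background lists the outcomes. The only ones that are events come at the end: "psychological distress, major adverse cardiovascular and cerebral events (MACCE) and hospital readmission rates". Under Outcome evaluation, these two "will be monitored from enrollment to the study to 3 months after the intervention through record review".

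The Background also says that sarcopenia is associated with "increased incidents of falls and fractures, functional decline and increased all-cause mortality".

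The section on the intervention group describes what participants do:
- On session content: "The core exercise session will comprise balance and resistance (40 minutes) training".
- On everyday practice: "they are suggested to perform a tandem stance while watching television, and then upgraded to standing on one leg". Daily self-practice is encouraged throughout.
- On supervision after the Week 9 booster visit: "The remaining sessions in this phase will all be unsupervised self-practice sessions".
- On symptoms: "Patients' symptom status will also be monitored and the exercise intensity will be titrated to ensure patients are free from ischemic symptoms".

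Outcome evaluation also includes the Seattle Angina Questionnaire, with subscales for the stability and the frequency of angina, on the T0, T1 and T2 schedule. Data analysis provides for descriptive summaries of feasibility, acceptance and compliance. It does not mention safety.

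**The concern.** The population is one that the protocol itself links to falls and fractures, and the intervention asks these people to challenge their balance and work against resistance at home, partly alone. The most foreseeable harms are falls, strains, dizziness and musculoskeletal pain. Most of these need not produce a cardiac or cerebral event or a readmission, and those that do not have no form, definition or analysis in the plan.

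Two things are at stake. First, the pilot is meant to inform a full-scale trial, and it could conclude that the programme is feasible with no systematic information on these harms. Second, the informal routes by which harms might come to light exist in the intervention arm only: specialist sessions, calls in Weeks 10 to 12, the logbook and the qualitative interviews. If anyone later set such reports against the control arm, the comparison would be distorted by unequal ascertainment.

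**Working it through.** The point rests on what is collected and not on a figure in the plan. The one plan figure used below is the arm size: 40 participants at 1:1 gives 40 / 2 = 20 per arm, as stated under Study setting and participants.

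**Step 1. Could any planned data source record a fall, injury or non-anginal symptom?**

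| Source (section) | Arms | What it records | Falls, injuries, non-anginal symptoms? |
|---|---|---|---|
| Record review (Outcome evaluation) | Both | MACCE, readmission | Only if the event leads to one of these; no cause coding described |
| Seattle Angina Questionnaire (Outcome evaluation) | Both | Angina, as 0–100 subscale scores | No, but angina is covered |
| Symptom monitoring (intervention group) | Intervention | Ischemic symptoms, to titrate intensity | No form, definition or analysis given |
| Training response forms (Fidelity monitoring) | Intervention | Not defined | Not stated |
| Video (Fidelity monitoring) | Intervention | Face-to-face and supervised sessions | Does not cover self-practice |
| Logbook (intervention group) | Intervention | Exercise pattern | No event field stated |
| Calls, Weeks 10–12 (intervention group) | Intervention | Support and guidance | No event questions stated |
| Interviews (Study setting and participants) | Intervention | Feasibility and acceptability | Not stated |

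No row collects these events in both arms unless they lead to MACCE or readmission.

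**Step 2. How much scheduled exercise is unsupervised?** From Table 1:
- Supervised: 8 (Weeks 1–4) + 2 (Weeks 5–6) + 1 (Week 9) = 11.
- Unsupervised, two sessions in every week: 2 (Weeks 5–6) + 4 (Weeks 7–8) + 1 (Week 9) + 6 (Weeks 10–12) = 13, so 13 / 24 = 54%.
- Unsupervised, counting each single-entry week once, as printed: 2 + 2 + 1 + 3 = 8, so 8 / 19 = 42%.

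The text gives two sessions per week for supervised sessions. Table 1 shows one entry in Weeks 7, 8 and 10–12, which may be a merged cell, so both counts are possible. Daily self-practice comes on top of either.

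**Step 3. What could a pilot of this size show if events were collected?**
- Expected number: if 10–20% of participants fell over the six months (an assumption; the documents give no rate), 20 × 0.10 = 2 to 20 × 0.20 = 4 per arm.
- Chance of at least one event among 20, 1 − (1 − p)^20, for assumed true risks p of 2%, 5%, 10% and 20%: 33%, 64%, 88% and 99%.
- Exact two-sided 95% upper bound with no events, 1 − 0.025^(1/n): 16.8% for n = 20. With 10% loss (n = 18, an assumption) it is 18.5%, and with 20% loss (n = 16, an assumption) 20.6%.

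A form would probably reveal common harms. It could not establish safety.

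**The case against.** The strongest reply is that the plan is not blind to harm. MACCE and readmissions are followed in both arms, angina is scored in both arms at all three time points, and a fall that led to readmission would count as a readmission. Entry criteria exclude people with contraindications or limitations precluding exercise, the specialist observes the home environment, and training response is documented. The plan also makes no claim of safety and proposes no between-arm comparison of harms, and 20 per arm could not support one.

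Much of this stands, and it rules out several stronger readings that a reader might infer:
- That MACCE and readmissions are the only harm data, or that exertional chest symptoms go unseen. The Seattle Angina Questionnaire contradicts both as far as angina is concerned.
- That most scheduled sessions are unsupervised. This holds at two sessions per week throughout (54%) but not as Table 1 is printed (42%). Unsupervised practice dominates only if daily self-practice is counted.
- That the protocol treats falls and fractures as the chief harms of sarcopenia. It lists them with functional decline and mortality.
- That few falls would reach a hospital record. The documents give no figure for this, and the point does not need one.

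The reply does not identify any planned record, in either arm, of falls, injuries or non-anginal symptoms that stop short of MACCE or readmission. Eligibility screening and home observation may lower risk, but they do not measure it.

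**Conclusion.** The gap is real and specific. No adverse-event collection is planned; falls, injuries and non-anginal symptoms short of MACCE or readmission are missed in both arms; and safety is not among the feasibility measures. This follows from the text and needs no numerical assumption. The likely count, 2 to 4 fallers per arm, depends entirely on the assumed 10–20% risk.

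A reader might go further and infer that the pilot would declare the programme safe, or that adding a form would let it do so. Neither is supported: the plan claims feasibility and preliminary effects only, and even complete capture with no events in 20 leaves risks up to about 17% open. The case for the change is that it is cheap, and that events not asked about during follow-up cannot be reliably recovered later. It should be made, but it does not invalidate the trial.

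**What to change.** Before the first T1 visit, add one short form, identical in both arms, at T1 and T2. It should ask about the period since the last visit and cover:
- falls;
- fractures, injuries or strains, noting whether care was needed, so that minor ones are still counted;
- non-anginal symptoms on exertion, such as dizziness or musculoskeletal pain. Angina can be left to the Seattle Angina Questionnaire.

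Have it self-completed, or asked after all performance tests, so that an answer revealing the allocation cannot influence the scoring of the primary outcome.

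In Data analysis, name safety as a descriptive outcome. Report the number of participants with at least one event per arm with exact 95% confidence intervals, and state that 0 of 20 leaves an upper bound of about 17% and so cannot establish safety. Keep incidental reports from sessions, calls, logbooks and interviews out of the between-arm figures, since the control arm has no counterpart.

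The cost is a slightly longer visit (each is planned at about 30 minutes), recall over roughly three months, which will miss some minor events, and a small unblinding risk. No added visits or staff are needed, and treatment, eligibility and sample size are unchanged.

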This study will recruit subjects in Care for Your Heart, a cardiac patient mutual support organization. Patients fulfilling the following eligibility criteria will be invited to join the study: 1) Chinese adults with a confirmed diagnosis of CAD; 2) age ≥ 60 years or older; 3) presence of sarcopenia according to the diagnostic criteria defined by the Asian Working Group for Sarcopenia²²: low skeletal muscle mass (measuring the appendicular skeletal muscle mass with bioelectrical impedance analysis: <7.0 kg/m² for men and <5.7 kg/m² for women), accompanied by low muscle strength (handgrip strength <28 kg for men and <18 kg for women); 4) free from ischemic symptoms when performing activities of daily living; 5) living in the community. Patients who cannot read Chinese or with impaired cognition (Abbreviated Mental Test score ≤ 6) or communication, a pacemaker or implantable cardioverter defibrillator precluding the use of bioelectrical impedance analysis for body composition assessment, physical limitations precluding exercise training, with any contraindication for exercise, any terminal or unstable conditions (e.g., malignant arrhythmia, severe aortic stenosis, cancer), admitted or recently completed a structured cardiac rehabilitation program within the past 6 months will be excluded.

The sample size for this pilot study was estimated based on the primary outcome (i.e., functional capacity) to be measured by the Short Physical Performance Battery (SPPB). The literature indicated the minimal clinically importance difference is >1 point of SPPB²³ and the SD estimate is 4.2 in the population with cardiovascular disease, giving rise to the standardized effect size as 0.28. According to the method proposed by Whitehead et al.,²⁴ a sample size of 20 per study arm for the pilot study would give the future main trial 80% power at 5% level of significance to detect the between-group changes in the primary outcome at post-intervention time points. The total sample size is therefore 40. They will be randomly allocated in a 1:1 ratio, to receive the strength-building intervention or usual care. All participants in the intervention group will be invited to take part in a face-to-face qualitative interview to explore the feasibility and acceptability of the intervention. The interviews will be conducted individually in the center of the Care For Your Heart. Each interview will be audio-recorded and will last for approximately 60 minutes.

Control group: Usual care

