Various methods will be used to monitor and optimize the fidelity of the study intervention. Assessments and record forms will be use to document the exercise prescription and progression. Participants’ attendance, exercise dose, performance and training response will be documented. A standardized manual will be developed to guide the delivery of each education session. The manual will also delineate the principles of exercise prescription and progression. Moreover, the 30% of the intervention sessions will be randomly selected

for fidelity monitoring by the principal investigator. Face-to-face sessions, in-person and remotely supervised sessions will be videotaped with participants' consent. Two post-doctoral fellows, who will be independent of the team will review the recorded videos and complete a performance checklist. The collected data will be used to evaluate the feasibility of the intervention.

Outcome evaluation

The following measuring tools/methods will be used for outcome evaluation at baseline (T0), immediate post-intervention (T1), and 3 months post-intervention (T2). Physical performance will be the primary outcome, while the rest will be the secondary outcomes.

Physical performance: The Short Physical Performance Battery³¹ will be used to assess physical performance and is well validated and widely adopted in clinical and research settings. It is a brief performance-based assessment consisting of 3 timed-tasks, including standing balance, walking speed, and chair stand tests. The timed results will be rescaled to obtain a score ranging from 0 to 12, higher scores indicate better physical performance.

Muscle mass and strength: The appendicular skeletal muscle mass (ASM) will be measured with the bioelectrical impedance analysis (In-Body). This is one of the gold-standard evaluation tools suggested by international guidelines for assessment of muscle mass. It is widely used in research and hospital setting for clients with sarcopenia. The muscle strength will be measured with a hydraulic dynamometer (Jamar). The standard protocol suggested by international guidelines will be followed, the maximum reading of at least 2 trials using the dominant hand in a maximum-effort isometric contraction will be recorded.

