Care For Your Heart, and posters in the center. A research assistant will screen the eligibility of the potential participants at the center of Care for Your Heart by measuring the calf circumference to identify patients with possible sarcopenia. A non-elastic measuring tape will be used to measure both calves, those individuals with the maximum value meeting the guideline-specified cut-offs (<34 cm in male; <33 cm in female) will be invited to undergo a more in-depth evaluation according to the eligibility criteria of this study. All eligible patients will be invited to participate. After obtaining the written informed consent, the research assistant will collect the baseline data (T0), then he/she will randomly assign participants into the intervention or control group with block randomization to ensure even distribution of participants in the two study groups over the study period. Patients will be allocated chronologically in a 1:1 ratio by using a computer-generated random sequence to determine the block size (4, 6 and 8) and respective study group allocation. The group allocation will be determined according to the random sequence codes placed in sealed opaque envelopes. Participants in the intervention group will receive the strength-building intervention whereas the control group will receive usual care. To minimize biases, another independent research assistant who is blinded to the group allocation will be responsible for collecting post-intervention data at another two time points (T1 and T2) in the center of the Care For Your Heart. Each assessment will last for approximately 30 minutes.

Data analysis

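### The research assistant who screens and takes the effort-based baseline tests also makes the assignment, so someone keeping a tally could guess the next arm about two times in three

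*Combined protocol and SAP*

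**What the plan says.** All of the procedure is in the section Data collection procedure and randomization.

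- **Screening:** "A research assistant will screen the eligibility of the potential participants". The same sentence says this is done by measuring calf circumference. Those below the cut-off go on to a fuller evaluation, for which no assessor is named.
- **Baseline and assignment:** once written consent is in hand, "the research assistant will collect the baseline data (T0), then he/she will randomly assign participants into the intervention or control group".
- **Sequence:** allocation is chronological and 1:1. A computer-generated sequence is used to "determine the block size (4, 6 and 8) and respective study group allocation". The codes are kept in sealed opaque envelopes. The plan does not say who generates the sequence, who holds the envelopes, or whether they are numbered.
- **Follow-up:** a different assistant, blinded to group, collects T1 and T2 only.
- **Limit on selection:** everyone found eligible is to be invited.

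The tests concerned depend on effort. Outcome evaluation says of the SPPB: "It is a brief performance-based assessment consisting of 3 timed-tasks". For grip, "the maximum reading of at least 2 trials using the dominant hand in a maximum-effort isometric contraction will be recorded". Grip also decides entry under Study setting and participants ("handgrip strength <28 kg for men and <18 kg for women"). That section also lists exclusions that call for judgement: "physical limitations precluding exercise training, with any contraindication for exercise".

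**The concern.** The plan separates roles after randomization but not before it. The person who makes the assignments learns each result, and nothing withholds earlier results while the next participant is being screened and tested. Opaque envelopes hide the next code, but they do not hide the tally of past ones. In a permuted-block sequence that tally carries information about what comes next.

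Two things are at stake. The first is enrolment: an assistant who expects a particular arm could, without intending it, time an approach or press for consent differently. The second is measurement: encouragement during the T0 SPPB or grip test could vary with the expected arm. The second matters more here, because T0 is one of the three time points in the repeated-measures comparison of changes. A blinded assessor at T1 and T2 cannot correct an error already recorded at T0, and neither can analysis by intention to treat.

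**Working it through.** **Inputs from the documents:** N = 40 (Study setting and participants); 1:1 chronological allocation, block sizes 4, 6 and 8, no strata mentioned (Data collection procedure and randomization). **Assumptions:** the three sizes are equally likely, and one person follows all 40 results. The documents state no predictability figure, so there is none to reproduce.

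**Step 1: guessing rule.** Guess the arm that is currently behind, and toss a coin when the arms are level.

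**Step 2: exact check on one block of 4.** Chance of a correct guess by position:
- 1st: 0.5 (level).
- 2nd: 2/3, since two of the three remaining places belong to the other arm.
- 3rd: (2/3 × 0.5) + (1/3 × 1) = 2/3, since the arms are level with probability 2/3 and otherwise the result is forced.
- 4th: 1.

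The sum is 0.5 + 0.667 + 0.667 + 1 = 2.833, and 2.833 / 4 = 70.8%. The same enumeration gives 68.3% for blocks of 6 and 66.6% for blocks of 8.

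**Step 3: the planned design.** In 40,000 simulated sequences, with sizes drawn at random from 4, 6 and 8 and cut at 40, the mean correct rate was 67.6%. That is 0.676 × 40 = 27 correct, against 20 by chance. The 5th to 95th percentiles were 62.5% to 72.5%, or 25 to 29 of 40.

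The rate is the same whether the guesser knows only the tally, the set of sizes, or the size of each block. Every complete block ends level, so the arm behind overall is the arm behind in the current block, and it is the better guess whatever that block's size.

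**Step 4: what varying the block size does achieve.** It reduces certainty.

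| Quantity | Share | Of 40 |
|---|---|---|
| Fully determined, sizes in use hidden | 2.3% | 0.9 |
| Fully determined, each size known | 23.6% | 9.4 |
| Guessable with probability at least 75%, sizes hidden | about 35% | about 14 |

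**Step 5: which changes help.**
- Past results withheld from the recruiting and baseline assistant: 50%, or 20 of 40.
- Central allocation with that assistant still learning each result: 67.6%, unchanged.
- Larger fixed blocks with results visible: 65.4% for blocks of 10 and 61.8% for blocks of 20.

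Withholding the results is therefore the part that matters.

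**Step 6: route to the estimate.** Write recorded T0 as true T0 + e, where e depends on the arm expected. Then change = T1 − (true T0 + e), so −e stays in the change however well T1 is blinded. A difference in true level appears in both T0 and T1 and largely cancels. If e is +δ when one arm is expected and −δ when the other is, the arms differ by 2 × δ × (2 × 0.676 − 1) = 0.70δ. The documents give no value for δ.

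**The case against.** The strongest reply is that the procedure already limits the harm. Most entry gates are numeric: age, calf circumference, muscle mass, grip and the cognition score. All eligible patients are invited. Recruitment by newsletter, social media and posters limits control over who comes forward and when. Few assignments are certain while the block sizes in use stay hidden, and the 68% needs someone to keep a tally, which nothing in the documents shows would happen. All of this stands as a limit on selective enrolment. It does not cover timing, persuasion at consent, the open number of grip trials (at least two), or encouragement at T0.

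Three stronger readings are tempting, and the documents do not support them.

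- **A bias in SPPB points.** A reader might assume that the assistant favours patients 0.5 points better or worse according to the expected arm. That gives 0.70 × 0.5 = 0.35 points, about a third of the plan's 1-point minimal important difference. The shift is invented, and a shift of 0.1 gives 0.07. SPPB is not an entry criterion and is measured after consent, so no score is available when deciding whom to enrol. A true baseline difference would also largely cancel in the comparison of changes. For scale, the plan's SD of 4.2 with 20 per arm gives a chance baseline difference with standard error 4.2 × √(2/20) = 1.33 points.
- **One person does everything.** That this assistant obtains consent is inferred from the sentence structure. That one assistant enrols all 40, and so sees every allocation, is also inferred. Nothing says that this assistant judges the exercise-related exclusions.
- **Enrolment is being steered.** The calculation shows what an attentive person could achieve, not that anyone does it.

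**Conclusion.** The point holds as a weakness in a stated procedure. The role that screens and takes effort-dependent baseline measurements also assigns, and so learns past allocations. The next arm is then guessable about 68% of the time instead of 50%. Random block sizes and opaque envelopes do not lower that average, although only about 1 assignment in 40 is certain when sizes are hidden. The figure rests on equally likely block sizes and on one person following all 40 results.

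The route that remains open and reaches the primary analysis most directly is differential encouragement at T0. Its size cannot be derived from the documents, and no fraction of the minimal important difference should be attached to it. This is a cheap improvement worth making, particularly because the pilot is meant to inform a full-scale trial that may carry the procedure forward.

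**What to change.** Amend Data collection procedure and randomization so that:

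1. an existing team member who neither recruits nor assesses (for example in the investigator's office) holds the sequence and the sequentially numbered envelopes;
2. that person opens the next envelope only after the T0 record is complete, and tells the participant and the exercise specialist the result;
3. the assistant who recruits and takes baseline measurements is not told allocations, past or current.

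The third item is essential, because moving custody alone leaves the guess rate at 67.6%. The order of T0 before assignment is already in the plan and stays.

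The cost is a wording change, about 40 messages and a short delay between T0 and notification. It assumes that a suitable team member is available, which the documents do not confirm. Some allocations may still leak at the shared center, so 50% is the target and not a guarantee.
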